10.2 Clinical Laboratory Evaluations

With the exception of urine pregnancy tests, a central laboratory will be used for all protocol-specified clinical laboratory parameters. Laboratory results reported in conventional units will be converted to International System of Units (SI) for all summaries and listings for consistent results presentation.

Safety laboratory including hematology, chemistry, thyroid function tests and HbA1c values and change from Baseline values will be summarized by visit and treatment group for each treatment period using descriptive statistics. For fasting glucose and HbA1c, means and 95% CI of the test results measured at each scheduled visit will be plotted.

The laboratory assessment will be categorized as low, normal or high based on normal ranges. Shift tables using categories of low, normal and high from Baseline (i.e., based on normal reference ranges) to each post-baseline visit will be generated by treatment group for each treatment period for hematology, chemistry parameters, thyroid function and HbA1c, respectively.

The laboratory assessment will be graded using the NCI-CTCAE (v4.03) grading scale, when available. A shift table for glucose by NCI-CTCAE grade and visit will be generated by treatment group. Another table with summary of incidence of \geq Grade 3 glucose will be provided.

For those patients who experienced hyperglycemia (per AE reporting), their safety laboratory assessment results during the double-masked treatment period will be examined and summarized using the similar manner described above.

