### 9.3 Selection of Trial Population

#### 9.3.1 Inclusion Criteria

Eligible patients must meet provide all the following criteria:

1. Written informed consent.
2. Male or female at least 18 years old at Screening.
3. Initial diagnosis of TED ≥2 years but <10 years prior to Screening. Clinical diagnosis of stable, chronic (inactive) TED, as determined by patient medical records indicating a CAS ≤1 in both eyes for at least 1 year prior to Screening or all of the following:
  - a. no progression in proptosis for at least 1 year prior to Screening
  - b. if patient has history of diplopia due to TED, no progression in diplopia for at least 1 year prior to Screening
  - c. no new inflammatory TED symptoms for at least 1 year prior to Screening.
4. CAS ≤1 at the Screening and Baseline Visits.
5. Proptosis >3-mm increase from the patient's baseline (prior to diagnosis of TED), as estimated by treating physician and/or proptosis >3 mm above normal for race and gender.
6. Patients must be euthyroid with the patient's baseline disease under control or have mild hypo- or hyperthyroidism (defined as free thyroxine and free triiodothyronine levels <50% above or below the normal limits) at Screening. Every effort should be made to correct the mild hypo- or hyperthyroidism promptly and to maintain the euthyroid state for the full duration of the trial.
7. Does not require immediate surgical ophthalmological intervention and is not planning corrective surgery/irradiation during the course of the trial.
8. Diabetic patients must have HbA1c ≤8.0% at Screening.
9. Patients with a history of inflammatory bowel disease, ulcerative colitis or Crohn's disease must be in clinical remission for at least 3 months, with no history of bowel surgery within 6 months prior to screening and no planned surgery during the trial. Concomitant stable therapies for inflammatory bowel disease without modifications in the 3 months prior to Screening are allowed.

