#### **Risk of Hyperglycemia**

- In nonclinical studies, there was no *in vitro* cross-reactivity of teprotumumab with the insulin receptor. Clinical trials in Active TED have shown a higher incidence of hyperglycemia in patients treated with teprotumumab compared to placebo. Patients with pre-existing diabetes mellitus (who were under appropriate glycemic control upon trial entry) or impaired glucose tolerance were more likely to experience an event of hyperglycemia after exposure to teprotumumab.

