#### **Management of Patients with Diabetes Mellitus**

- Patients with known controlled diabetes mellitus are allowed to participate in trials with teprotumumab. HbA1c levels should be monitored every 6 weeks in these patients.
- Investigators are strongly encouraged to adjust their patients' diabetes management to maintain HbA1c levels ~8%. In the event a patient's HbA1c level rises to >8% while in the trial, the Investigator must assess the risk versus benefit for the patient to remain in the trial, discuss with sponsor's medical monitor or designee, and document the decision.

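### HbA1c shifts are tabulated only as low, normal or high, and no planned table counts by arm the patients who exceed the protocol's 8% level

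*SAP*

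**What the plan says.** **Shift tables.** SAP 10.2 plans "Shift tables using categories of low, normal and high from Baseline (i.e., based on normal reference ranges) to each post-baseline visit", by treatment group and "for each treatment period for hematology, chemistry parameters, thyroid function and HbA1c, respectively". Protocol 9.6.5 has the same low, normal and high scheme.

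**Graded tables.** SAP 10.2 also states: "The laboratory assessment will be graded using the NCI-CTCAE (v4.03) grading scale, when available". The graded outputs it then names are for glucose only: "A shift table for glucose by NCI-CTCAE grade and visit will be generated by treatment group", and "Another table with summary of incidence of" glucose values of Grade 3 or higher. No HbA1c table by grade or by threshold is named.

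**Other HbA1c outputs.** SAP 10.2 plans by-visit descriptive statistics of value and change from Baseline, and a plot of means with 95% confidence intervals. SAP 5 defines descriptive statistics to include quartiles and maximum, and promises listings of the raw data. SAP 10.2 adds a separate laboratory summary, for the double-masked period, of patients with a reported hyperglycemia event.

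**The 8% level.** Criterion 8 in Protocol 9.3.1 reads "Diabetic patients must have HbA1c" of at most 8.0% at Screening. SAP 15.1, footnote 16, carries the same limit. For the trial itself, Protocol 9.5.3.1.1.5 says "In the event a patient's HbA1c level rises to >8% while in the trial", the investigator must weigh risk against benefit, discuss the case with the medical monitor and document the decision. The same section says that patients with diabetes or impaired glucose tolerance "were more likely to experience an event of hyperglycemia after exposure to teprotumumab".

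**The concern.** The protocol names both the patients at higher risk and the HbA1c level that calls for a documented decision. The only categorical HbA1c table uses neither. It separates patients at the reference limit, and many diabetic patients are likely to be above that limit when they enter. For them the table has no cell into which a deterioration can move.

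Among patients who start within range, a small rise just over the limit and a rise to 9% fall in the same normal-to-high cell.

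At stake is how clearly a known risk is reported. The study report would not state how many patients in each arm went above 8%. That number would have to be taken from listings, after unmasking and without a prespecified definition.

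**Working it through.** The plan states no figure for this point. Its arm sizes (38 and 19; Protocol 9.6.7, SAP 5.1) serve as denominators, assuming that all randomized patients are dosed and measured. The reference limit and the number of diabetic patients are not in the documents, so both are assumptions below.

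**1. Classification.** Take the rule: high if HbA1c exceeds the upper reference limit. With assumed limits of 5.7, 6.0, 6.5, 7.0 and 7.4%, the values 7.5%, 8.1% and 10% are all high each time. For any limit below 7.5%, a patient moving from 7.5% to 10% is high to high, and passing 8% leaves no mark in the shift table. This does not hold for a diabetic patient whose Baseline is within range. That patient would show normal to high.

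**2. Mean and mean plot.** Movement of the arm mean = (patients × rise) / arm size.
- One patient rising 2.5 points on TEPEZZA: 2.5/38 = 0.07 points.
- One such patient on placebo: 2.5/19 = 0.13 points.
- Three such patients on TEPEZZA: 3 × 2.5/38 = 0.20 points.

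**3. Maximum and third quartile.** A by-visit maximum above 8% says that at least one patient exceeded it. A third quartile above 8% says that about a quarter of the arm did (0.25 × 38 = 9.5 patients). These two statistics do not separate the numbers in between. Being by-visit, they also do not say whether a high value at Week 12 and one at Week 24 belong to the same patient.

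**4. What a count would show.** For the 38-patient arm, with illustrative counts and exact 95% intervals:
- 1 patient: 1/38 = 2.6% (0.1 to 13.8)
- 3 patients: 3/38 = 7.9% (1.7 to 21.4)
- 5 patients: 5/38 = 13.2% (4.4 to 28.1)

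**5. Size of the diabetic group.** If 10 to 20% of patients are diabetic, there are 3.8 to 7.6 (about 4 to 8) on TEPEZZA and 1.9 to 3.8 (about 2 to 4) on placebo.

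**6. Sampling.** Protocol 9.5.3.1.1.5 asks for HbA1c every 6 weeks in diabetic patients. The double-masked visit lists take it at Screening and Day 1, then at Week 12 but not at Weeks 6 or 18 (9.5.6.2.3), and at Week 24 (9.5.6.2.5). Footnote 16 of the Schedule of Assessments adds repeats about every 90 days for clinically significant elevations. Under SAP 5.4.3, when several continuous results fall in one visit window, the one closest to the target day is used. A repeat value above 8% can therefore drop out of a by-visit table.

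**The case against.** The strongest case against is that the plan already makes these patients visible.

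- **Maxima and listings.** A 10% value can appear as the arm maximum, and a 2.5-point rise as the maximum change. Listings give every value.
- **Hyperglycemia subset.** The separate laboratory summary for patients with a hyperglycemia event is much less diluted than an arm mean of 38.
- **Neighbouring tables.** The glucose grade shift, the Grade 3 or higher glucose table and the AESI table (SAP 10.1.6) sit beside the HbA1c shift table.
- **Endpoints.** Protocol 9.6.1.4 names Grade 3 or higher fasting glucose and change in HbA1c as safety endpoints. It does not name incidence above 8%. The 8% rule is a case-by-case management trigger that the protocol does not ask to be tabulated.
- **Version.** The SAP introduction bases it on protocol V4.0. The Summary of Changes shows the on-trial 8% text as added in V5.0.

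Most of this stands. A reader might infer that deterioration in diabetic patients would be hidden, or that a flat shift table would be taken as reassurance. The documents do not support that, because these other outputs can reveal individual cases. A reader might also infer that the SAP overlooked a rule in its own source protocol. The version dates do not support that for the on-trial rule; only the 8.0% entry limit was already in the SAP.

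What the objection does not supply is the count. The hyperglycemia subset depends on an event having been reported, covers one period and reuses the same categories. The AESI and glucose tables count event terms and glucose values, not HbA1c.

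**Conclusion.** The concern holds as a limited gap in descriptive safety reporting. The HbA1c shift categories cannot register a rise in a patient who starts above the reference limit, and no unredacted table gives the number of patients per arm who exceed 8%.

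The size is modest. Each patient above 8% is 2.6% of the TEPEZZA arm, and a few such patients hardly move the mean. How many patients are affected cannot be derived from the documents. The high-to-high example needs a reference limit below 7.5%, and the figure of 4 to 8 diabetic patients on TEPEZZA rests on an assumed share of 10 to 20%.

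The SAP grades laboratory results where a grade is available, but the documents do not say whether HbA1c has one. Safety data are summarized without hypothesis testing (SAP 10), so significance level, power and the primary analysis are unaffected. The change is worth making because it is cheap and uses the protocol's own level.

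**What to change.** In SAP 10.2:

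1. Replace the HbA1c shift categories with three: within or below the reference range; above the range up to 8.0%; above 8.0%.
2. Add, by treatment group and treatment period, the number and percentage of patients with any on-treatment HbA1c above 8.0%, whether scheduled or repeat. State the denominator and define on-treatment so that the End-of-Treatment sample counts. Week 24 falls 21 days after Week 21 and has a window of ±7 days, so a 21-day limit could exclude it.
3. Optionally, list these patients or split the count by diabetic status at Baseline, defined from medical history. The SAP has no such variable at present, and the strata will be very small.

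Separately, update the SAP to protocol V5.0, and reconcile the passages on HbA1c sampling in diabetic patients (every 6 weeks in 9.5.3.1.1.5 against the visit lists). An ever-above-8.0% count depends on how often HbA1c is measured.

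The cost is SAP wording, a recategorised table and one small extra table from laboratory data already collected. The safety picture may look slightly less favourable. A rise that stays within one of the new bands will still show only in the change-from-Baseline summaries and listings.

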10.3 Vital Sign and Weight Measurements

Vital signs measurements will include systolic and diastolic blood pressures, heart rate, respiratory rate, height, weight, BMI and temperature.

Descriptive summaries of observed and change from Baseline values will be presented for each vital sign parameter by treatment group and visit for each treatment period.

A summary table for weight loss and a shift table for hypertension by NCI-CTCAE grade will be generated by treatment group and visit for each treatment period.

10.4 Other Safety Data

Pregnancy test will be performed at each scheduled visit and the data will be included in a by-subject listing.

For best-corrected visual acuity (BCVA), shift tables for study and fellow eye each will be presented providing the count of patients with each type of finding (i.e., Normal, Mild, Moderate Low Vision, Severe Low Vision and Blindness) at each assessment visit by treatment group for each treatment period. BCVA findings are categorized as follow:

- Normal: 20/12 to 20/40
- Mild: worse than 20/40 to 20/70
- Moderate Low Vision: worse than 20/70 to 20/200
- Severe Low Vision: worse than 20/200 to 20/400
- Blindness: worse than 20/400

11. Immunogenicity: Anti-drug Antibody

ADA samples will be collected prior to the infusion at scheduled visits. If the ADA test is positive after confirmatory and reactive titer testing, the sample will then be tested for neutralizing antibodies (NAb).

Overall positive ADA result for a patient will be defined as at least one post Day 1 confirmed positive ADA result. Cumulative negative result will be defined as negative ADA result at all available time points for a patient.

The reported titer (ratio) value is the minimum required dilution (1:2) * the dilution factor used.

Titer (Ratio) – reported value	Titer (Result) – converted value
1:<2	2
1:x	X

For example, x could be 4, 10, 40, 64, and 100.

The incidence and titer of positive ADA results will be summarized by visit and treatment group using descriptive statistics for the safety analysis set in each treatment period.

All ADA and NAb test results will be presented in a by-subject listing for the safety analysis set in each treatment period.

12. Pharmacokinetics

Pharmacokinetic samples will be collected pre-dose and at the end of infusion on scheduled visits, Day 1, Weeks 3 and 12 of the double-masked treatment period (all patients) and at Weeks 24, 27 and 36 (non-responders who elect to receive open-label TEPEZZA); a single sample will also be collected at Week 24 (or premature withdrawal [PW1]) of the double-masked treatment period (proptosis responders and proptosis non-responders who elect not to receive open-label TEPEZZA) and Week 48 of the open-label treatment period (non-responders who elect to receive open-label TEPEZZA).

A patient listing of serum concentration-time data will be presented by visit. Teprotumumab peak and trough (i.e., prior to dose) concentrations will be summarized by visit and ADA status (overall positive vs cumulative negative; only to be performed if more than 2 patients receiving TEPEZZA treatment with a positive ADA observed in the trial) using descriptive statistics. The analyses will be based on the PK analysis set in each treatment period.

Further, the mean and CV% (calculated as 100%*SD/mean) of pre-dose serum concentrations will be provided by visit in the subset of patients who are confirmed ADA positive, NAb positive (if applicable) and ADA negative for each visit. This analysis will be provided for the PK Population.

13. Changes in the Planned Analysis

- To ensure the control of the overall Type I error rate in analyzing multiple efficacy endpoints, the process to test individual efficacy endpoints has been added in the SAP section 5 and section 9, as an addition to the protocol.
- TEPEZZA Baseline is defined in the SAP for analysis relative to baseline in the open-label treatment period.
- TEPEZZA study day is defined in the SAP for analysis relative to first dose date during the open-label treatment period.

- To better characterize GO-QoL, analyses of patients with minimal clinically important change in the GO-QoL subscales will be provided.
- Summary and shift tables for chemistry (excluding glucose) will be based on all records (fasting and non-fasting records).

14. References

Heitjan DF and Little RJA. Multiple Imputation for the Fatal Accident Reporting System. *Journal of the Royal Statistical Society, Series C*. 1991; 40:13–29.

Rubin DB. *Multiple Imputation for Nonresponse in Surveys*. New York: John Wiley & Sons. 1987.

Schenker N and Taylor JMG. Partially parametric techniques for multiple imputation. *Computational Statistics & Data Analysis*. 1996; 22:425-446.

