### 9.3.2 Exclusion Criteria

Patients will be ineligible for trial participation if they meet **any** of the following criteria:

1. Decreased best-corrected visual acuity due to optic neuropathy, defined by a decrease in vision of 2 lines on the Snellen chart, new visual field defect or color defect secondary to optic nerve involvement within the last 6 months.
2. Corneal decompensation unresponsive to medical management in the study eye.
3. Decrease in proptosis of  $\geq 2$  mm in the study eye between Screening and Baseline.
4. Prior orbital irradiation or orbital decompression in the study eye.
5. Prior strabismus surgery.
6. Alanine aminotransferase or aspartate aminotransferase  $>3 \times$  the upper limit of normal or estimated glomerular filtration rate  $\leq 30$  mL/min/1.73 m^2 at Screening.
7. Use of any steroid (IV, oral, steroid eye drops) for the treatment of TED or other conditions within 3 weeks prior to Screening. Steroids cannot be initiated during the trial. Exceptions include topical and inhaled steroids and steroids used to treat infusion reactions.
8. Any treatment with rituximab (Rituxan® or MabThera®) within 12 months prior to the first infusion of trial drug or tocilizumab (Actemra® or Roactemra®) within 6 months prior to the first infusion of trial drug. Use of any other non-steroid immunosuppressive agent within 3 months prior to the first infusion of trial drug.
9. Any previous treatment with TEPEZZA, including previous enrollment in this trial or participation in a prior teprotumumab trial.
10. Treatment with any mAb within 3 months prior to Screening.
11. Identified pre-existing ophthalmic disease that, in the judgment of the Investigator, would preclude trial participation or complicate interpretation of trial results.

12. Use of an investigational agent for any condition within 60 days or 5 half-lives, whichever is longer, prior to Screening or anticipated use during the course of the trial.
13. Malignant condition in the past 12 months (except successfully treated basal/squamous cell carcinoma of the skin or cervical cancer *in situ*).
14. Pregnant or lactating women.
15. Current drug or alcohol abuse or history of either within the previous 2 years, in the opinion of the Investigator or as reported by the patient.
16. Known hypersensitivity to any of the components of TEPEZZA or prior hypersensitivity reactions to mAbs.

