#### **9.5.3.6 Visual Acuity**

Best-corrected visual acuity will be assessed at Screening, Day 1 and Weeks 6, 12, 18, and 24 (or PW1) and at Weeks 30, 36, 42 and 48 (or PW2) (non-responders who elect to receive open-label TEPEZZA) (see Section 2.1).

If significant abnormalities are noted compared with previous visits, including a loss of 2 lines or more of vision or other abnormalities not otherwise specified but of concern to the ophthalmologist, further investigations of visual function will be conducted according to the ophthalmologist's decision.

New findings reported from on-trial visual acuity assessments will not be reported as AEs if, according to the Investigator, the abnormalities are unequivocally due to disease progression and should only be reported as AEs if they fulfill any of the SAE criteria or are the reason for discontinuation of trial drug.

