#### 9.6.5 Safety and Tolerability Analyses

The number and percentage of patients experiencing at least 1 occurrence of a TEAE, SAE, TEAE resulting in premature discontinuation of treatment and AFSI for each unique System Organ Class and Preferred Term will be summarized by treatment group. TEAEs and SAEs will also be summarized by severity and relationship to trial drug, as assessed by the Investigator. Grade 3 and higher TEAEs, as graded by the National Cancer Institute Common Terminology Criteria for Adverse Events (NCI-CTCAE), will also be summarized for each unique System Organ Class and Preferred Term.

The number and percentage of patients in each treatment group using concomitant medications will be summarized by Anatomical Therapeutic Chemical Level 4 term and Preferred Term.

For best-corrected visual acuity, shift tables will be presented providing the count of patients in each treatment group with each type of finding (normal, abnormal – not clinically significant, or abnormal – clinically significant) at Baseline compared to each postbaseline visit.

Descriptive summaries of observed and change from Baseline values will be presented for each vital sign parameter by treatment group and visit. A shift table for vital signs by NCI-CTCAE grade and visit will be generated by treatment group.

Safety laboratory (hematology and fasting chemistry [including thyroid panel and HbA1c]) values and change from Baseline will be summarized by visit and treatment group using descriptive statistics. The laboratory assessment will be categorized as low, normal or high based on normal ranges and graded using the NCI-CTCAE grading scale, when available. Shift tables using categories of low, normal and high from Baseline to each visit will be generated by treatment group. Additionally, a shift table for glucose by NCI-CTCAE grade and visit will be generated by treatment group. Summaries will be provided separately for hyperglycemia.

The rate and titer of positive ADA samples will be summarized by visit and treatment group using descriptive statistics. Teprotumumab peak and trough (i.e., prior to dose) concentrations will also be summarized by visit using descriptive statistics.

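### The banded visual-acuity shift table can show a loss of 2 or more lines as no change, and no planned table counts line losses by arm

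*SAP*

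**What the plan says.** Best-corrected visual acuity is a stated safety endpoint (protocol 9.6.1.4, SAP 3.2.4), worded only as its results, with no line-change measure.

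Protocol 9.6.5 plans the summary: "For best-corrected visual acuity, shift tables will be presented providing the count of patients in each treatment group with each type of finding". It gives the findings as "normal, abnormal – not clinically significant, or abnormal – clinically significant) at Baseline compared to each postbaseline visit".

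SAP 10.4 also plans shift tables: "shift tables for study and fellow eye each will be presented providing the count of patients with each type of finding". Its findings are five fixed bands. The top one is "Normal: 20/12 to 20/40" and the next is "Mild: worse than 20/40 to 20/70". The others are Moderate Low Vision (to 20/200), Severe Low Vision (to 20/400) and Blindness. SAP section 7 uses the same five bands for the baseline description.

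Protocol 9.5.3.6 says which abnormalities, compared with previous visits, lead to further investigation, "including a loss of 2 lines or more of vision". Exclusion criterion 1 in protocol 9.3.2 uses the same size of change, "defined by a decrease in vision of 2 lines on the Snellen chart".

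SAP section 13 lists five changes to the planned analysis. The change of visual-acuity categories is not among them.

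**The concern.** A shift table shows only movement between its categories. The top band here is wide compared with the 2-line change that the protocol treats as significant. An eye can therefore lose 2 lines or more and still be counted as Normal at Baseline and Normal afterwards. A smaller loss that happens to cross 20/40 is counted as a shift. The table follows the position of the cut-points more than the size of the loss.

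Adverse-event tables fill the gap only in part. Under protocol 9.5.3.1.1.1, a new acuity finding is not an adverse event if the Investigator relates it to thyroid eye disease and not to trial drug. Under 9.5.3.6, the same applies if it is unequivocally disease progression, unless it is serious or the reason for stopping trial drug. A loss attributed to the disease could then be absent from the adverse-event tables and also produce no shift in the acuity table.

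What is at stake is whether the report of a stated safety endpoint would show a difference between arms in moderate acuity loss.

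**Working it through.** **Inputs from the documents.** The five bands (SAP 10.4); the 2-line size of change (protocol 9.5.3.6 and 9.3.2); the Snellen chart as the reference for lines (protocol 9.3.2). There is no plan figure to reproduce, because neither document quantifies line loss.

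**Assumption.** The documents do not define a line. I take one line as 0.1 logMAR, so that

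lines lost = 10 × [log10(end denominator / 20) − log10(start denominator / 20)].

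As a cross-check I counted rows on an assumed Snellen sequence: 20/12, 15, 20, 25, 30, 40, 50, 60, 70, 80, 100, 200, 400.

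| Change | Lines (logMAR) | Rows | Bands | Shown as a shift? |
|---|---|---|---|---|
| 20/25 to 20/40 | 10 × log10(40/25) = 2.0 | 2 | Normal to Normal | No |
| 20/20 to 20/40 | 10 × log10(40/20) = 3.0 | 3 | Normal to Normal | No |
| 20/15 to 20/40 | 10 × log10(40/15) = 4.3 | 4 | Normal to Normal | No |
| 20/12 to 20/40 | 10 × log10(40/12) = 5.2 | 5 | Normal to Normal | No |
| 20/40 to 20/50 | 10 × log10(50/40) = 1.0 | 1 | Normal to Mild | Yes |
| 20/30 to 20/50 | 10 × log10(50/30) = 2.2 | 2 | Normal to Mild | Yes |

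**How much of the scale is affected.** For each starting row I checked whether a fall of 2 or 3 rows stays in one band, on three assumed charts. The short Snellen sequence is 20/15, 20, 25, 30, 40, 50, 70, 100, 200, 400.

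| Assumed chart | 2-row loss hidden | 3-row loss hidden |
|---|---|---|
| Short Snellen sequence | 3 of 8 | 2 of 7 |
| Snellen sequence above | 6 of 11 | 3 of 10 |
| 0.1-logMAR chart, 20/12.5 to 20/400 | 8 of 14 | 5 of 13 |

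On both Snellen sequences every hidden 3-row loss lies in Normal, in eyes that start at 20/20 or better. On the logMAR chart three of the five lie in Normal and two in Moderate Low Vision. These are counts of starting rows, not of patients. The documents give no baseline acuity distribution, so the proportion of patients affected is unknown.

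**The two plans side by side.** Under protocol 9.6.5 a fall from 20/20 to 20/40 could be classed as abnormal and clinically significant, and so appear as a shift. Under SAP 10.4 it cannot. Neither plan includes a count of line losses or a change-from-Baseline summary for acuity. Laboratory values and vital signs both get change-from-Baseline summaries (SAP 10.2 and 10.3).

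**The case against.** The case for leaving the plan as it is has five parts.

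- **The 2-line rule is a prompt at the site.** It compares with previous visits, leads to investigation at the ophthalmologist's decision, and does not ask for a tabulation. The exclusion criterion is an entry rule tied to optic neuropathy. This stands. A reader might infer that the SAP breaks an analysis threshold set by the protocol, but the protocol sets none. The 2-line figure only shows what size of loss the protocol regards as significant.
- **The bands do detect losses.** A reader might infer that the table cannot detect a 2-line or 3-line loss at all. That is not supported, because losses that cross a band edge register. The fault is limited to losses within a band.
- **The losses are not hidden from the trial.** SAP section 5 puts the raw data behind the tables into listings, and with about 57 patients they can be read. This stands, but a listing gives no count by arm.
- **Suspected drug effects still reach the adverse-event tables.** This stands too. The exemptions cover only findings attributed to the disease, and serious findings or those that stop trial drug are reported even so.
- **The endpoint as worded is met, and the SAP's bands are explicit where the protocol's categories were left to judgement.** This is fair. It does not explain why the replacement is missing from section 13, and explicit cut-points do not prevent a line count as well.

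**Conclusion.** The point holds as a minor weakness in the reporting of one safety endpoint. The only planned post-baseline summary of acuity can show losses of 2 to about 5 lines as no change when they fall inside the Normal band, while showing a loss of about 1 line across 20/40 as a shift. Separately, the SAP replaced the protocol's categories without recording it in section 13.

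The line counts rest on the 0.1-logMAR assumption. Row counting on an ordinary Snellen sequence gives the same picture, so the direction does not depend on that choice, though exact line numbers depend on the chart. The number of patients affected cannot be estimated from the documents. That no line-loss table is planned is a statement about the readable text. The documents do not support a claim that acuity losses would go unrecorded or that the primary efficacy conclusions are affected.

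**What to change.** 1. In SAP 10.4, add a table by eye, visit and treatment group of the number and percentage of patients with a loss of 2 lines or more from Baseline, using the acuity values already needed to assign the bands. State how lines are derived: either chart rows, or logMAR with one line as 0.1.
2. Note that the comparison is with Baseline, in line with the other safety summaries. It therefore does not reproduce the protocol's site-level prompt, which compares with previous visits.
3. Keep the five-band shift table alongside it.
4. Record in SAP section 13 that the five bands replace the clinical-significance categories of protocol 9.6.5, with the reason.

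The cost is one derived variable, one extra table and one line in section 13. No new data are collected and no clinical rule changes.
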